7.2.3 Pregnancy

Females must be instructed to stop taking the study medication and immediately inform the investigator if pregnancy occurs during the study. Pregnancies occurring up to 6 months after the completion of the study medication must also be reported to the investigator. The investigator should report all pregnancies within 24 hours to the sponsor.

The investigator should counsel the patient; discuss the risks of continuing with the pregnancy and the possible effects on the fetus. Monitoring of the patient should continue until conclusion of the pregnancy.

Pregnancy occurring in the partner of a male patient participating in the study should also be reported to the investigator and the sponsor. The partner should be counseled and followed as described above.

Women of childbearing potential, defined as all women physiologically capable of becoming pregnant, can be included in the study provided they are using highly effective methods of contraception during dosing and for 6 months after the last dose of tebentafusp or Investigator's Choice.

Highly effective contraception methods include the following:

- Total abstinence from sexual relations for the duration of the treatment when applicable to the lifestyle of the patient. Periodic abstinence (eg, calendar, ovulation, symptothermal, post-ovulation methods) and withdrawal are not acceptable methods of contraception.
- Female sterilization (have had surgical bilateral oophorectomy with or without hysterectomy) or tubal ligation at least 6 weeks before taking study treatment. In case of oophorectomy alone, this applies only when the reproductive status of the woman has been confirmed by follow-up hormone level assessment.
- Male sterilization (at least 6 months prior to Screening). For female patients on the study, the vasectomized male partner should be the sole partner for that patient.
- The combination of any 2 of the following methods when both are used simultaneously:
 - Use of oral, injected, or implanted hormonal methods of contraception or other forms of hormonal contraception that have comparable efficacy (failure rate < 1%), for example hormone vaginal ring or transdermal hormone contraception

- Placement of an intrauterine device or intrauterine system
- Barrier methods of contraception: condom or occlusive cap (diaphragm or cervical/vault caps) when used with spermicidal foam, gel, film, cream, or used of a spermicidal vaginal suppository

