In case of use of oral contraception, women should have been stable on the same oral contraceptive pill for a minimum of 3 months before beginning treatment on this study.

Women are considered post-menopausal and not of childbearing potential if they have had 12 months of natural (spontaneous) amenorrhea with an appropriate clinical profile (eg, age appropriate, history of vasomotor symptoms), or have had surgical bilateral oophorectomy (with or without hysterectomy) or tubal ligation at least 6 weeks prior to study treatment. In the case of oophorectomy alone, only when the reproductive status of the woman has been confirmed by follow-up hormone level assessment is she considered not of childbearing potential.

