10.1.3 Screening

All aspects of the screening evaluation must be completed prior to entering the study, unless otherwise noted. The following must be completed within 28 days of starting treatment:

- Signed main study informed consent for study participation
- Confirmation of disease: documented presence of unresectable and/or locally advanced clear cell sarcoma, including pathologic confirmation and measurable disease by RECIST 1.1 with demonstration of progression within 6 months of registration (if not newly diagnosed)

- Full medical history including all active conditions
- Review of concomitant medications including any relevant prior medications taken
- Physical exam (including height and weight)
 - Note: height may be documented at any time prior to registration
- Vital signs (pulse, blood pressure, temperature, respiratory rate, and oxygen saturation).
- ECOG performance status
- Complete blood count with differential
- Comprehensive metabolic panel (sodium, potassium, chloride, bicarbonate, BUN, creatinine, glucose, total protein, albumin, total bilirubin, total protein, AST, ALT, alkaline phosphatase, calcium), magnesium, and phosphorus
- Amylase, lipase, CK, and LDH
- PT (or INR) and aPTT
- Thyroid function tests (TSH, T4 free, T3)
- HIV-1/2 antibody test, Hepatitis B surface antigen and core antibody, and Hepatitis C antibody, with reflex PCR test if positive
- Urinalysis (dipstick)
- Serum β -HCG or urine pregnancy test for women of child-bearing potential. If the urine test is positive or cannot be confirmed as negative, a serum pregnancy test is required
- 12-lead electrocardiogram (ECG)
- CT scan of the chest (with or without contrast), CT abdomen and pelvis (with contrast, unless contraindicated) or MRI abdomen pelvis (with and without contrast, unless contraindicated, and CT or MR of other known sites of disease, as clinically indicated
- Research biopsy
- Research blood collection

Laboratory and radiological assessments performed as part of standard of care prior to signing the informed consent may be used if performed within the screening time window (28 days prior to C1D1).

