10.2 ON STUDY EVALUATIONS

All the assessments required as part of the study are indicated in the Study Calendar organized by visit date, with assessments required indicated with an “X” at the specific visits when they should be performed. Assessments required on C1D1 that are performed as part of the screening evaluations and within 72 hours prior to the first dose of study treatment do not need to be repeated on C1D1.

The following procedures will be performed during the treatment period:

C1D1

- Physical exam (short)
- Vital signs (Please see section 10.5)
- Relevant laboratory evaluations
 - Complete blood count with differential
 - Comprehensive metabolic panel (sodium, potassium, chloride, bicarbonate, BUN, creatinine, glucose, total protein, albumin, total bilirubin, total protein, AST, ALT, alkaline phosphatase, calcium), magnesium, and phosphorus
 - Amylase, lipase, CK, and LDH
 - PT (or INR) and aPTT
- Concomitant medications
- Administration of tebentafusp
- Recording of adverse events

CXD8, CXD15:

- Vital signs (Please see section 10.5)
- Concomitant medications
- Administration of tebentafusp
- Recording of adverse events

Cycle 2:

- Physical exam (short one, with weight)
- Vital signs (Please see section 10.5)
- Relevant laboratory evaluations
 - Complete blood count with differential
 - Comprehensive metabolic panel (sodium, potassium, chloride, bicarbonate, BUN, creatinine, glucose, total protein, albumin, total bilirubin, total protein, AST, ALT, alkaline phosphatase, calcium), magnesium, and phosphorus
 - Amylase, lipase, CK, and LDH
 - PT (or INR) and aPTT
- Concomitant medications
- Administration of tebentafusp
- Recording of adverse events
- Research blood

Cycle 3, etc.:

- Physical exam (short)

- Vital signs (pulse, blood pressure, temperature, respiratory rate)
- Relevant laboratory evaluations
 - Complete blood count with differential
 - Comprehensive metabolic panel (sodium, potassium, chloride, bicarbonate, BUN, creatinine, glucose, total protein, albumin, total bilirubin, total protein, AST, ALT, alkaline phosphatase, calcium), magnesium, and phosphorus
 - Amylase, lipase, CK, and LDH
- PT (or INR) and aPTT
- Concomitant medications
- Thyroid function tests (D1 of odd cycles)
- Recording of adverse events
- Administration of tebentafusp
- Recording of adverse events

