- Serum β -HCG or urine pregnancy test for women of child-bearing potential. If the urine test is positive or cannot be confirmed as negative, a serum pregnancy test is required
- Radiographic assessment
 - Occurring every 6 weeks through 48 weeks, and then every 9 weeks thereafter
- Research blood (C3D1, C5D1, C9D1 only)
- Research biopsy (Cycle 3 only)

NOTE: All visits can be obtained ± 2 day of stated time point. Laboratory assessments may occur up to 2 days before infusion. Consecutive infusions of tebentafusp must be administered at least 5 days apart.

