2 At screening and C1D1, prior to dosing, a complete physical examination will be completed. From C1D8 onwards, a short physical examination will be performed. Starting with C4D1, patients will have short physical examination performed only on day 1 of the cycle and at EOT

3 Inpatient hospitalization and frequent vital signs (at a minimum of every 4 hours [\pm 30 min] or more frequently according to institutional standards) are required at C1D1, C1D8, and C1D15. Inpatient monitoring at Cycle 2 Day 1 and beyond will be determined based on the toxicity observed in the individual patient in C1D1-C1D15. Patients experiencing a grade 2 or greater hypotension event at C1D15 must be observed as an inpatient for the subsequent C2D1 dose.

4 Thyroid function studies to be completed on Day 1 of every odd-numbered cycle at Cycle 3 and beyond, as well as at EOT

5 Pregnancy testing required every 6 weeks and at EOT in all WOCBP

6 Radiographic assessment via CT or MR (where CT is not feasible or per the investigator's discretion) will occur at baseline and every subsequent 6 weeks through 48 weeks, and then every 9 weeks thereafter. Progression of disease by RECIST 1.1 within 24 weeks is required for enrollment, unless the patient has a new diagnosis of CCS.

7 Mandatory biopsies are required at baseline within 28 days of study initiation and again after two cycles of treatment at C3 (+/- 7days). Biopsy at progression will be optional.

8 Research blood will be collected at baseline (during study screening or on C1D1 prior to initiating treatment), C2D1, C3D1, C5D1, C9D1, and end of treatment.

9 Tebentafusp will be administered on the scheduled day (\pm 2 days), and consecutive infusions of tebentafusp must be administered at least 5 days apart.

10 Survival follow-up should be completed every 12 weeks until death or until the end of the study is reached.

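### No pregnancy test is scheduled between screening and C3D1, so the first dose can rest on a 28-day-old result and the sixth infusion on a 63-day-old one

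*Protocol*

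**What the plan says.** - **Screening (Protocol 10.1.3).** The serum or urine pregnancy test belongs to the general screening list, headed "The following must be completed within 28 days of starting treatment". It has no shorter window of its own. Standard-of-care laboratory results from the same 28 days are also accepted.
- **On treatment (Protocol 10.2).** The lists for C1D1, for Days 8 and 15, and for Cycle 2 contain no pregnancy test. The "urine pregnancy test for women of child-bearing potential" first reappears in the list for Cycle 3 onward, with no frequency. The thyroid entry in that same list does have one: "Thyroid function tests (D1 of odd cycles".
- **C1D1 repeats (Protocol 10.2).** Assessments required on C1D1 that were done "within 72 hours prior to the first dose of study treatment do not need to be repeated on C1D1". Blood counts and chemistry are on the C1D1 list; the pregnancy test is not, so this rule does not reach it.
- **Study Calendar.** The pregnancy-test row is marked at Screening, Cycle 3+ and EOT only. Footnote 5 reads "Pregnancy testing required every 6 weeks and at EOT in all WOCBP". Footnote 4, for thyroid tests, is anchored: "Thyroid function studies to be completed on Day 1 of every odd-numbered cycle at Cycle 3 and beyond".
- **Related rules.** Exclusion 3.2.16 bars pregnant women. Section 7.2.3 admits women of childbearing potential who are "using highly effective methods of contraception during dosing and for 6 months after the last dose of tebentafusp" and tells a woman who becomes pregnant to stop the drug. Section 7.5 states that there are no data in pregnant women, that no animal reproductive or developmental studies have been done, and that transfer to the fetus is unknown.

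**The concern.** Pregnancy is an exclusion that can change unnoticed during a 28-day screening window, and a simple laboratory test can check it. The protocol repeats counts and chemistry at C1D1 but not this test. A pregnancy that begins after the screening test, or is too early for that test to detect, could be exposed to the first dose and to the rest of Cycles 1 and 2 before any scheduled test finds it. A site that doses on a 28-day-old negative result commits no deviation.

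Footnote 5 adds an ambiguity. Counted from C1D1, its six weeks end at C3D1, where the calendar places the next test, but no test is done on the day the count starts. Counted from the screening test, the calendar can break the footnote's own interval. Section 10.2 gives no frequency from Cycle 3 onward, so read alone it would mean a test every 21 days.

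The group concerned is unlikely to be negligible. Section 2.1 cites a series of 141 patients with a median age of 27 years at diagnosis and slightly more women than men. The protocol gives no count of women of childbearing potential.

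**Working it through.** The protocol states no figure for the age of the test at dosing, so there is none to reproduce. The check is calendar arithmetic.

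**Inputs**
- Maximum time from screening test to C1D1: *s* = 28 days (10.1.3).
- Weekly infusions on Days 1, 8 and 15 of a 21-day cycle (Section 5 and Table 1 in 8.2).
- Next scheduled test: C3D1 (10.2 and the calendar), which is 2 × 21 = 42 days after C1D1.
- Footnote 5 interval: 6 × 7 = 42 days.

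**Formulas**
- Age of the test at infusion *k* (*k* = 1 to 6) = *s* + 7(*k* − 1).
- Gap between the screening test and the C3D1 test = *s* + 42.

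**Results on the nominal schedule**

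| Infusion | Visit | Age, test on day −28 | Age, test on day −1 | Age with a C1D1 test (*s* = 0 to 3) |
|---|---|---|---|---|
| 1 | C1D1 | 28 | 1 | 0 to 3 |
| 2 | C1D8 | 35 | 8 | 7 to 10 |
| 3 | C1D15 | 42 | 15 | 14 to 17 |
| 4 | C2D1 | 49 | 22 | 21 to 24 |
| 5 | C2D8 | 56 | 29 | 28 to 31 |
| 6 | C2D15 | 63 | 36 | 35 to 38 |
| Gap to C3D1 | | 70 | 43 | 42 to 45 |

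**When a result is older than 42 days at dosing.** Solving *s* + 7(*k* − 1) > 42:
- infusion 6 if *s* > 7;
- infusion 5 if *s* > 14;
- infusion 4 if *s* > 21.

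Infusions 1 to 3 cannot exceed 42 days on the nominal schedule.

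**Windows and delays.** The ±2-day dosing window can take infusion 6 to 63 + 2 = 65 days. Longer delays add more, because Section 5 moves study assessments (radiology excepted) along with a delayed infusion.

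**The other reading of footnote 5.** Counting six weeks from a day −28 test gives −28 + 42 = 14 days after C1D1, which is C1D15. Neither 10.2 nor the calendar schedules a pregnancy test at that visit.

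**The case against.** The strongest reply is that a repeat interval is naturally counted from the last test. On that reading of footnote 5, a day −28 test falls due again at C1D15, and no infusion rests on a result older than about 42 days. Blank calendar cells do not settle the matter, because other footnotes add to the grid: footnote 2 requires a short physical examination from C1D8, and footnote 8 allows research blood on C1D1, where those cells are blank. This is a fair point about ambiguity. It does not prevail, because the visit lists in 10.2 also omit a C1D15 test, and the C3D1 test fits a count from C1D1. The 28-day-old result at first dose stands on either reading.

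Second, other safeguards exist. Women must use highly effective contraception, and pill users "women should have been stable on the same oral contraceptive pill for a minimum of 3 months before beginning treatment". Pregnancy, or the intention to become pregnant, ends treatment. The women's contraception rules refer to the treatment or dosing period, whereas the men's rule in 3.2.18 starts at enrollment. Even so, 7.2.3 can fairly be read as requiring contraception already in use at inclusion. The point does not depend on settling that: contraception lowers the risk but does not verify status.

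Third, a C1D1 test has its own detection limit. A conception shortly before C1D1 could still go undetected through six infusions. This stands: later exposure is reduced, not removed.

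Fourth, the protocol sets no maximum test age before dosing, and 10.2 and the calendar grid agree with each other. That is also true. The point concerns a weak schedule and an unanchored footnote, not a contradiction between sections.

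**Conclusion.** The point holds. As scheduled, the first dose can rest on a pregnancy test 28 days old and the sixth infusion on one 63 days old, with 70 days between tests. These are permitted worst cases, assuming the earliest allowed screening test and on-time dosing; a day −1 test gives 1, 36 and 43 days. The 63- and 70-day figures also take footnote 5 as counted from C1D1, which is what 10.2 and the calendar imply. The 28-day figure does not depend on that reading. How many women are affected cannot be estimated from the protocol. No endpoint, sample size or decision rule is touched. It is a patient-safety weakness that should be corrected because correction is cheap.

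**What to change.** 1. Keep the screening test.
2. Add the existing urine or serum test to the C1D1 pre-dose list in 10.2 and mark it in the calendar. Apply the 72-hour allowance already in 10.2, and require a negative result before the first dose.
3. Reword footnote 5 on the model of footnote 4: testing at C1D1 before dosing (or in the preceding 72 hours), then on Day 1 of each odd-numbered cycle from Cycle 3, that is, every six weeks from C1D1, and at EOT.
4. Put the same frequency beside the test in the 10.2 list for Cycle 3 onward.

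A further test at C2D1 is optional. It would make the result about 14 days old at the sixth infusion.

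**Cost.** One calendar mark, one added bullet, one reworded footnote and a frequency note. Each woman of childbearing potential has one extra test at a visit that already includes laboratory work, unless her screening test fell within 72 hours of dosing. A positive or unclear urine result could delay C1D1 until a serum test is read.

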11. MEASUREMENT OF EFFECT

11.1 Antitumor Effect – Solid Tumors

For the purposes of this study, patients should be re-evaluated for response every 6 weeks.

Response and progression will be evaluated in this study using the new international criteria proposed by the revised Response Evaluation Criteria in Solid Tumors (RECIST) guideline (version 1.1)¹. Changes in the largest diameter (unidimensional measurement) of the tumor lesions and the shortest diameter in the case of malignant lymph nodes are used in the RECIST criteria. Response will also be evaluated using Choi criteria (see reference), which takes changes in tumor size and density into consideration for radiographic response².

11.1.1 Definitions

Evaluable for toxicity. All patients will be evaluable for toxicity from the time of their first treatment with *tebentafusp*.

Evaluable for objective response. Only those patients who have measurable disease present at baseline, have received at least one cycle of therapy, and have had their disease re-evaluated will be considered evaluable for response. These patients will have their response classified according to the definitions stated below. (Note: Patients who exhibit objective disease progression prior to the end of cycle 1 will also be considered evaluable.)

Evaluable Non-Target Disease Response. Patients who have lesions present at baseline that are evaluable but do not meet the definitions of measurable disease, have received at least one cycle of therapy, and have had their disease re-evaluated will be considered evaluable for non-target disease. The response assessment is based on the presence, absence, or unequivocal progression of the lesions.

11.1.2 Disease Parameters

Measurable disease. Measurable lesions are defined as those that can be accurately measured in at least one dimension (longest diameter to be recorded) as ≥ 20 mm by chest x-ray or as ≥ 10 mm with CT scan, MRI, or calipers by clinical exam. All tumor measurements must be recorded in millimeters (or decimal fractions of centimeters).

Note: Tumor lesions that are situated in a previously irradiated area might or might not be considered measurable. *If the investigator thinks it appropriate to*

include them, the conditions under which such lesions should be considered must be defined in the protocol.

Malignant lymph nodes. To be considered pathologically enlarged and measurable, a lymph node must be ≥ 15 mm in short axis when assessed by CT scan (CT scan slice thickness recommended to be no greater than 5 mm). At baseline and in follow-up, only the short axis will be measured and followed.

Non-measurable disease. All other lesions (or sites of disease), including small lesions (longest diameter <10 mm or pathological lymph nodes with ≥ 10 to <15 mm short axis), are considered non-measurable disease. Bone lesions, leptomeningeal disease, ascites, pleural/pericardial effusions, lymphangitis cutis/pulmonitis, inflammatory breast disease, and abdominal masses (not followed by CT or MRI), are considered as non-measurable.

Note: Cystic lesions that meet the criteria for radiographically defined simple cysts should not be considered as malignant lesions (neither measurable nor non-measurable) since they are, by definition, simple cysts.

‘Cystic lesions’ thought to represent cystic metastases can be considered as measurable lesions, if they meet the definition of measurability described above. However, if non-cystic lesions are present in the same patient, these are preferred for selection as target lesions.

Target lesions. All measurable lesions up to a maximum of 2 lesions per organ and 5 lesions in total, representative of all involved organs, should be identified as **target lesions** and recorded and measured at baseline. Target lesions should be selected on the basis of their size (lesions with the longest diameter), be representative of all involved organs, but in addition should be those that lend themselves to reproducible repeated measurements. It may be the case that, on occasion, the largest lesion does not lend itself to reproducible measurement in which circumstance the next largest lesion which can be measured reproducibly should be selected. A sum of the diameters (longest for non-nodal lesions, short axis for nodal lesions) for all target lesions will be calculated and reported as the baseline sum diameters. If lymph nodes are to be included in the sum, then only the short axis is added into the sum. The baseline sum diameters will be used as reference to further characterize any objective tumor regression in the measurable dimension of the disease.

Non-target lesions. All other lesions (or sites of disease) including any measurable lesions over and above the 5 target lesions should be identified as **non-target lesions** and should also be recorded at baseline. Measurements of these lesions are not required, but the presence, absence, or in rare cases unequivocal progression of each should be noted throughout follow-up.

11.1.3 Methods for Evaluation of Measurable Disease

All measurements should be taken and recorded in metric notation using a ruler or calipers. All baseline evaluations should be performed as closely as possible to the beginning of treatment and never more than 4 weeks before the beginning of the treatment.

The same method of assessment and the same technique should be used to characterize each identified and reported lesion at baseline and during follow-up. Imaging-based evaluation is preferred to evaluation by clinical examination unless the lesion(s) being followed cannot be imaged but are assessable by clinical exam.

Clinical lesions Clinical lesions will only be considered measurable when they are superficial (*e.g.*, skin nodules and palpable lymph nodes) and ≥ 10 mm diameter as assessed using calipers (*e.g.*, skin nodules). In the case of skin lesions, documentation by color photography, including a ruler to estimate the size of the lesion, is recommended.

Chest x-ray Lesions on chest x-ray are acceptable as measurable lesions when they are clearly defined and surrounded by aerated lung. However, CT is preferable.

Conventional CT and MRI This guideline has defined measurability of lesions on CT scan based on the assumption that CT slice thickness is 5 mm or less. If CT scans have slice thickness greater than 5 mm, the minimum size for a measurable lesion should be twice the slice thickness. MRI is also acceptable in certain situations (*e.g.* for body scans).

Use of MRI remains a complex issue. MRI has excellent contrast, spatial, and temporal resolution; however, there are many image acquisition variables involved in MRI, which greatly impact image quality, lesion conspicuity, and measurement. Furthermore, the availability of MRI is variable globally. As with CT, if an MRI is performed, the technical specifications of the scanning sequences used should be optimized for the evaluation of the type and site of disease. Furthermore, as with CT, the modality used at follow-up should be the same as was used at baseline and the lesions should be measured/assessed on the same pulse sequence. It is beyond the scope of the RECIST guidelines to prescribe specific MRI pulse sequence parameters for all scanners, body parts, and diseases. Ideally, the same type of scanner should be used and the image acquisition protocol should be followed as closely as possible to prior scans. Body scans should be performed with breath-hold scanning techniques, if possible.

PET-CT At present, the low dose or attenuation correction CT portion of a combined PET-CT is not always of optimal diagnostic CT quality for use with RECIST measurements. However, if the site can document that the CT performed as part of a PET-CT is of identical diagnostic quality to a diagnostic CT (with IV and oral contrast), then the CT portion of the PET-CT can be used

for RECIST measurements and can be used interchangeably with conventional CT in accurately measuring cancer lesions over time. Note, however, that the PET portion of the CT introduces additional data which may bias an investigator if it is not routinely or serially performed.

Ultrasound Ultrasound is not useful in assessment of lesion size and should not be used as a method of measurement. Ultrasound examinations cannot be reproduced in their entirety for independent review at a later date and, because they are operator dependent, it cannot be guaranteed that the same technique and measurements will be taken from one assessment to the next. If new lesions are identified by ultrasound in the course of the study, confirmation by CT or MRI is advised. If there is concern about radiation exposure at CT, MRI may be used instead of CT in selected instances.

Endoscopy, Laparoscopy The utilization of these techniques for objective tumor evaluation is not advised. However, such techniques may be useful to confirm complete pathological response when biopsies are obtained or to determine relapse in trials where recurrence following complete response (CR) or surgical resection is an endpoint.

Tumor markers Tumor markers alone cannot be used to assess response. If markers are initially above the upper normal limit, they must normalize for a patient to be considered in complete clinical response. Specific guidelines for both CA-125 response (in recurrent ovarian cancer) and PSA response (in recurrent prostate cancer) have been published [JNCI 96:487-488, 2004; J Clin Oncol 17, 3461-3467, 1999; J Clin Oncol 26:1148-1159, 2008]. In addition, the Gynecologic Cancer Intergroup has developed CA-125 progression criteria which are to be integrated with objective tumor assessment for use in first-line trials in ovarian cancer [JNCI 92:1534-1535, 2000].

Cytology, Histology These techniques can be used to differentiate between partial responses (PR) and complete responses (CR) in rare cases (e.g., residual lesions in tumor types, such as germ cell tumors, where known residual benign tumors can remain).

The cytological confirmation of the neoplastic origin of any effusion that appears or worsens during treatment when the measurable tumor has met criteria for response or stable disease is mandatory to differentiate between response or stable disease (an effusion may be a side effect of the treatment) and progressive disease.

FDG-PET While FDG-PET response assessments need additional study, it is sometimes reasonable to incorporate the use of FDG-PET scanning to complement CT scanning in assessment of progression (particularly possible 'new' disease). New lesions on the basis of FDG-PET imaging can be identified according to the following algorithm:

a. Negative FDG-PET at baseline, with a positive FDG-PET at follow-up is

- a sign of PD based on a new lesion.*
- b. *No FDG-PET at baseline and a positive FDG-PET at follow-up: If the positive FDG-PET at follow-up corresponds to a new site of disease confirmed by CT, this is PD. If the positive FDG-PET at follow-up is not confirmed as a new site of disease on CT, additional follow-up CT scans are needed to determine if there is truly progression occurring at that site (if so, the date of PD will be the date of the initial abnormal FDG-PET scan). If the positive FDG-PET at follow-up corresponds to a pre-existing site of disease on CT that is not progressing on the basis of the anatomic images, this is not PD.*
 - c. *FDG-PET may be used to upgrade a response to a CR in a manner similar to a biopsy in cases where a residual radiographic abnormality is thought to represent fibrosis or scarring. The use of FDG-PET in this circumstance should be prospectively described in the protocol and supported by disease-specific medical literature for the indication. However, it must be acknowledged that both approaches may lead to false positive CR due to limitations of FDG-PET and biopsy resolution/sensitivity.*

Note: A 'positive' FDG-PET scan lesion means one which is FDG avid with an uptake greater than twice that of the surrounding tissue on the attenuation corrected image.

